6.2.2 Assessment of Relationship

6.2.2.1 Relationship to Investigational Product

The investigator is required to provide an assessment of relationship of AEs and SAEs to the investigational product.

An event will be considered “not related” to use of the investigational product if any of the following tests are met:

- An unreasonable temporal relationship between administration of the investigational product and the onset of the event (eg, the event occurred either before, or too long after, administration of the investigational product for it to be considered product-related)
- A causal relationship between the investigational product and the event is biologically implausible (eg, death as a passenger in an automobile accident)
- A clearly more likely alternative explanation for the event is present (eg, typical adverse reaction to a concomitant drug and/or typical disease-related event)

Individual AE/SAE reports will be considered “related” to use of the investigational product if the “not related” criteria are not met.

“Associated with the use of the drug” means that there is “a reasonable possibility” that the event may have been caused by the product under investigation (ie, there are facts, evidence, or arguments to suggest possible causation).

6.2.2.2 Relationship to Protocol Procedures

The investigator is also required to provide an assessment of relationship of SAEs to protocol procedures on the SAE Report Form. This includes nontreatment-emergent SAEs (ie, SAEs

that occur prior to the administration of investigational product) as well as treatment-emergent SAEs. A protocol-related SAE may occur as a result of a procedure or intervention required during the study (eg, blood collection, washout of an existing medication). The following guidelines should be used by investigators to assess the relationship of SAEs to the protocol:

Protocol related: The event occurred due to a procedure/intervention that was described in the protocol for which there is no alternative etiology present in the subject's medical record.

Not protocol related: The event is related to an etiology other than the procedure/intervention that was described in the protocol (the alternative etiology must be documented in the study subject's medical record).

6.3 Recording of Safety Parameters

6.3.1 Recording of Adverse Events and Serious Adverse Events

Adverse events will be recorded on the CRF using a recognized medical term or diagnosis that accurately reflects the event. Adverse events will be assessed by the investigator for severity, relationship to the investigational product, possible etiologies, and whether the event meets criteria of an SAE and therefore requires immediate notification to MedImmune Patient Safety. See Section 6.1.2 for the definition of SAEs, and Section 6.2.1 and Section 6.2.2 for guidelines for assessment of severity and relationship, respectively. If an AE evolves into a condition that meets the regulatory definition of "serious," it will be reported on the SAE Report Form.

6.3.2 Recording of Other Events of Special Interest

6.3.2.1 Hepatic Function Abnormality

Events of hepatic function abnormality (as defined in Section 6.1.3.1) should be recorded according to the definitions of AE and SAE (Section 6.1.1 and Section 6.1.2, respectively):

- If an event of hepatic function abnormality is a pre-existing condition, the event does not meet the definition of an AE and does not need to be recorded as such.

- If the etiology of the hepatic function abnormality is known (including progression of primary or metastatic malignancy) and/or not a pre-existing condition, the diagnosis should be recorded as an AE/SAE per Section [6.3.1](#).
- If the hepatic function abnormality remains unexplained, the term “hepatic function abnormal” should be used to report the AE/SAE per Section [6.4.2](#).

6.4 Reporting Requirements for Safety Parameters

6.4.1 Study Reporting Period and Follow-up for Adverse Events

The reporting period for AEs is the period immediately following the time that written informed consent is obtained through 30 days after the last dose of MEDI-565. New (nonserious) AEs that start after the reporting period will not be collected.

All AEs will be followed to resolution through the end of subject participation in the study, even if the date extends beyond the reporting period.

6.4.2 Reporting of Serious Adverse Events

6.4.2.1 Study Reporting Period and Follow-up for Serious Adverse Events

The reporting period for SAEs is the period immediately following the time that written informed consent is obtained through 30 days post the subject’s last dose of treatment or until the subject begins another anticancer therapy. After submitting an initial SAE report for a subject (to MedImmune Patient Safety), the investigator is required to follow the subject proactively and provide further information on the subject’s condition to MedImmune Patient Safety.

At any time after completion of the study, if an investigator or qualified designee becomes aware of an SAE that is suspected by the investigator or qualified designee to be related to investigational product, the event must be reported to MedImmune Patient Safety.

The investigator is responsible for following all SAEs until resolution, until the subject returns to baseline status, or until the condition has stabilized with the expectation that it will remain chronic, even if this extends beyond study participation.

6.4.2.2 Notifying the Sponsor of Serious Adverse Events

Within 24 hours of identifying an SAE, regardless of the presumed relationship to the investigational product, the investigator or qualified designee must complete the SAE Report Form and fax it to MedImmune Patient Safety.

MedImmune contact information:

Patient Safety
MedImmune
[name]
[name]
[contact]

The sponsor is responsible for reporting certain SAEs as expedited safety reports to applicable regulatory authorities, ethics committees, and participating investigators, in accordance with ICH Guidelines and/or local regulatory requirements (see Section [6.4.2.3](#)). The sponsor may be required to report certain SAEs to regulatory authorities within 7 calendar days of being notified about the event; therefore, it is important that investigators submit additional information requested by the sponsor as soon as it becomes available.

Investigators should provide all available information at the time of SAE Report Form completion. Investigators should not wait to collect additional information to fully document the event before notifying MedImmune Patient Safety of an SAE. When additional information becomes available, investigators should submit a follow-up SAE Report Form (separate from the initial report form) with the new information. Any follow-up information to an SAE also needs to be provided to MedImmune Patient Safety within 24 hours of learning of the new information.

6.4.2.3 Safety Reporting to Investigators, Institutional Review Boards or Independent Ethics Committees, and Regulatory Authorities

The sponsor is responsible for reporting all applicable SAEs to regulatory authorities, investigators, and IRBs/IECs, as applicable, in accordance with national regulations in the countries where the study is conducted. The sponsor will also prepare an expedited report for other safety issues where these might materially alter the current benefit-risk assessment of an investigational product or that would be sufficient to consider changes in the administration of the investigational product or in the overall conduct of the study.

The sponsor will prepare an expedited report for all SAEs that are unexpected and potentially related to the investigational product, and copies will be distributed to all concerned regulatory authorities, investigator(s), and IRBs/IECs according to applicable laws and regulations. The investigational site also will forward a copy of all expedited reports to the site's applicable IRB/IEC. Investigators must also submit safety information provided by the sponsor to the IRB/IEC as detailed in Section 10.1 and Section 10.2.

6.4.3 Other Events Requiring Immediate Reporting

6.4.3.1 Overdose

An overdose is defined as a subject receiving a dose of investigational product in excess of that specified in the Investigator's Brochure, unless otherwise specified in this protocol.

Any overdose of a study subject with the investigational product, with or without associated AEs/SAEs, is required to be reported within 24 hours of knowledge of the event to MedImmune Patient Safety using the Fax Notification Form (see Section 6.4.2.2 for contact information). If the overdose results in an AE, the AE must also be recorded on the AE CRF (see Section 6.3.1). Overdose does not automatically make an AE serious, but if the consequences of the overdose are serious, for example death or hospitalization, the event is serious and must be reported as an SAE (see Section 6.3.1 and Section 6.4.2).

6.4.3.2 Hepatic Function Abnormality

Hepatic function abnormality (as defined in Section 6.1.3.1) in a study subject, with or without associated clinical manifestations, where the etiology is unknown, is required to be reported as "hepatic function abnormal" *within 24 hours of knowledge of the event* to MedImmune Patient Safety using the Safety Fax Notification Form (see Section 6.4.2.2 for contact information). The investigator shall review the data with the medical monitor. The investigator should use clinical judgement to establish the cause based on local standard of care and follow the subject by conducting testing as clinically indicated. If, after appropriate workup, in the opinion of the investigator, the underlying diagnosis for the abnormality remains unexplained, discontinuation of dosing for this subject should be considered.

Each reported event of hepatic function abnormality will be followed by the investigator and evaluated by the sponsor. If the etiology of the event remains unconfirmed and/or is considered related to investigational product (see Section 6.2.2.1), a prompt cumulative

review of safety data and the circumstances of the event in question will be conducted and assessed by the MedImmune Safety Monitoring Committee (SMC) (see Section 6.5) to determine whether continued dosing of current study subjects and/or study entry should be interrupted, whether the protocol will be modified, or whether the study will be discontinued permanently. Review and approval by the SMC is required for resumption of subject dosing or study entry in the event that the study is interrupted. Where applicable, regulatory authorities and IRBs/IECs will be notified of any actions taken with the study.

6.4.3.3 Pregnancy

Pregnancy in a female subject who has received investigational product is required to be reported *within 24 hours of knowledge of the event* to MedImmune Patient Safety using the Fax Notification Form (see Section 6.4.2.2 for contact information).

Subjects who become pregnant during the study period must not receive additional doses of investigational product but will not be withdrawn from the study. After obtaining the subject's consent, the pregnancy will be followed for outcome of the mother and child (including any premature terminations) and should be reported to MedImmune Patient Safety after-outcome.

6.4.4 Study Reporting Period for Other Events of Special Interest

The following events are considered immediately reportable events and must be reported *within 24 hours of knowledge of the event* to MedImmune Product Safety using the Fax Notification Form:

- Any withdrawal of consent during the study
- Any treatment-related event resulting in discontinuation of investigational product, interruption of dosing, or delay in completion of a study treatment cycle

6.5 Safety Management During the Study

The MedImmune medical monitor has primary responsibility for the ongoing medical review of safety data throughout the study. This includes review of SAEs and timely review of AEs and "other events" reported during the study. MedImmune Patient Safety is responsible for the receipt, immediate review, investigation, and follow-up of SAEs and other immediately reportable events (eg, overdose and pregnancies) reported from the clinical study sites.

A study-specific Dose Escalation Committee will provide ongoing safety surveillance of the study, with regularly scheduled reviews of safety and other relevant data. This committee will be responsible for dose-escalation decisions and making recommendations regarding further conduct of the study. The Dose Escalation Committee includes the MedImmune medical monitor for the study, the MedImmune Patient Safety physician for the study, and the principal investigator from each actively enrolling study site. This committee will review data, including all AEs, laboratory parameters, pharmacokinetics, and pharmacodynamic data, following the full enrollment of any dose-escalation cohort and completion of the DLT evaluation period. This committee will also review data at other time points in response to AEs assessed as medically relevant by the medical monitor. Dose-escalation decisions and outcomes of reviews of safety and other relevant data will be communicated in writing to all participating sites and principal investigators. The sponsor will notify sites when enrollment into each dose cohort has been completed and when enrollment into the next dose cohort is permitted.

The MedImmune SMC (or equivalent) provides safety surveillance, guidance, and oversight for all clinical development trials in which MedImmune has sponsor accountabilities. The SMC (or equivalent) reviews protocol-specific safety data at regularly scheduled meetings and ad hoc meetings, and provides oversight for individual study protocol safety committees, such as those specified for early-phase dose-escalation trials. Based on review of safety data, the SMC (or equivalent) may suspend enrollment or subject dosing in clinical studies, request modification of study documents, or take other actions as deemed necessary.

7 Statistical Considerations

7.1 General Considerations

Data will be provided in data listings sorted by treatment group and subject number. Tabular summaries will be presented by treatment group. Categorical data will be summarized by the number and percentage of subjects in each category. Continuous variables will be summarized by descriptive statistics, including mean, standard deviation, median, minimum, and maximum. Confidence intervals (CIs) will be 2-sided, unless otherwise stated. Details of endpoint analyses will be described in the statistical analysis plan.

7.2 Analysis Populations

The Evaluable Population for DLT includes all subjects enrolled in the dose-escalation phase who received at least one full cycle of MEDI-565 and completed safety follow-up through the DLT evaluation period (defined in Section 4.5.4.5) or experience any DLT. The Evaluable Population for DLT will be used for the MTD evaluation.

The Safety Population includes all subjects who receive any investigational product.

The Per-Protocol Population will include all subjects who complete 2 cycles of treatment or discontinue treatment due to disease progression or toxicity.

7.3 Endpoints

7.3.1 Primary Endpoints

The primary endpoints are as follows:

- The number (percentage) of subjects with a DLT will be summarized by dose level and overall. The MTD evaluation will be based on the evaluable population for DLT.
- The OBD will be determined based upon analysis of all available subject data including safety, PK, pharmacodynamic, biomarker, and antitumor activity data.
- The number (percentage) of subjects with AEs and SAEs reported through 30 days after the last dose of MEDI-565 will be summarized for all subjects who received at least one dose of study drug (Safety Population). Adverse events and SAEs will be graded according to the [NCI CTCAE v4.03](#) and described by system organ class using the Medical Dictionary for Regulatory Activities (MedDRA) preferred term, severity, and relationship to MEDI-565. Frequency rates will be calculated for each system organ class and MedDRA preferred term.
- The number (percentage) of subjects with significant or important clinical findings in ECG will be summarized by dose cohort.
- The number (percentage) of subjects who had clinically significant laboratory changes recorded as AEs will be summarized. Laboratory hematology and chemistry values will be summarized with the worst value during the study by dose cohort. Clinically significant coagulation profile and urinalysis results will be described.

7.3.2 Secondary Endpoints

7.3.2.1 Pharmacokinetic Assessment

Individual MEDI-565 concentrations will be tabulated by dose cohort along with descriptive statistics. Noncompartmental PK data analysis will be performed for data obtained from each dose cohort with scheduled PK sample collection. If the data allow, descriptive statistics of noncompartmental PK parameters (AUC, C_{\max} , T_{\max} , CL, V_d , $t_{1/2}$) will be provided.

7.3.2.2 Immunogenicity Assessment

The immunogenic potential of MEDI-565 will be assessed by summarizing the number and percentage of subjects who develop detectable anti-drug antibodies. Immunogenicity results will be listed for each subject. The impact of anti-drug antibodies on PKPD, antitumor activity, and safety will be assessed if data allow.

7.3.2.3 Efficacy Assessments

Assessments of antitumor activity of MEDI-565 include ORR, TTR, DR, TTP, PFS, and OS. RECIST guidelines (v1.1; [Eisenhauer et al, 2009](#)) will be used to determine tumor response.

Objective Response Rate

Objective response rate is defined as the proportion of subjects with confirmed CR or confirmed PR according to RECIST guidelines. Confirmed responses are those that persist on repeat imaging study ≥ 4 weeks after the initial documentation of response. The 95% confidence interval of ORR will be estimated using the exact probability method.

Time to Response

Time to response will be measured from the start of MEDI-565 administration to the first documentation of response (CR or PR) and will only be assessed in subjects who have achieved objective response.

Duration of Response

Duration of response will be defined as the duration from the first documentation of objective response to the first documented disease progression. The DR will be censored on the date of last tumor assessment documenting absence of disease progression for subjects who have no

documented progression prior to data cutoff, dropout, or the initiation of alternate anticancer treatment. Duration of response will only be evaluated for the subgroup of subjects with an objective response using the Kaplan-Meier method ([Kaplan and Meier, 1958](#)).

Time to Progression

Time to progression will be measured from the start of treatment with MEDI-565 until the documentation of disease progression. Disease progression is defined according to RECIST guidelines v1.1 ([Eisenhauer et al, 2009](#)). The TTP will be censored on the date of last tumor assessment documenting absence of tumor progression for subjects who have no documented progression prior to data cutoff, dropout, or the initiation of alternate anticancer treatment. Subjects having no tumor assessments after the start of treatment with MEDI-565 will have TTP censored on the first date of treatment with MEDI-565. The TTP will be evaluated using the Kaplan-Meier method ([Kaplan and Meier, 1958](#)).

Progression-free Survival

Progression-free survival will be measured from the start of treatment with MEDI-565 until the documentation of disease progression or death due to any cause, whichever occurs first. Disease progression is defined according to RECIST guidelines. Progression-free survival will be censored on the date of last tumor assessment documenting absence of tumor progression for subjects who have no documented progression and are still alive prior to data cutoff, dropout, or the initiation of alternate anticancer treatment. Subjects having no tumor assessments after the start of treatment with MEDI-565 will have PFS censored on the first date of treatment with MEDI-565. PFS will be evaluated using the Kaplan-Meier method ([Kaplan and Meier, 1958](#)).

Overall Survival

Overall survival will be determined as the time from the start of treatment with MEDI-565 until death. For subjects who are alive at the end of study or lost to follow-up, OS will be censored on the last date when subjects are known to be alive. The OS will be evaluated using the Kaplan-Meier method ([Kaplan and Meier, 1958](#)).

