5.1 Efficacy and Clinical Pharmacology Parameters

5.1.1 Efficacy and Clinical Pharmacology Parameters

The PK parameters for MEDI-565 to be assessed include C_{max} , T_{max} , AUC, CL, V_d , and, $t_{1/2}$.

Immunogenicity of MEDI-565 will be evaluated by examining the presence of anti-MEDI-565 antibodies in blood samples.

The antitumor activity of MED-565 will be assessed using objective response rate (ORR), time to response (TTR), duration of response (DR), time to progression (TTP), progression-free survival (PFS), and overall survival (OS) using RECIST guidelines ([Eisenhauer et al, 2009](#)).

If radiographic changes are believed by the investigator to be secondary to drug induced inflammation and not tumor progression, the investigator may postpone a diagnosis of PD until the next scheduled radiographic evaluation in the study ([Wolchok et al, 2009](#)).

Biomarkers that will be evaluated in this study include, but are not limited to, flow cytometric analysis of whole blood for T cell, B cell and natural killer (NK) cell counts and subsets, circulating cytokines, circulating soluble protein markers (eg, CEA, nucleosomal DNA, M30/M65), circulating tumor cells, expression level of CEA protein and T-cell numbers in archival tumor tissue samples (if samples and assays are available).

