5.2.2.17 After Every 2 Cycles

- 1) Assess for AEs and SAEs
- 2) Update concomitant medications

- 3) Perform CXR, CT or MRI scan (disease assessments must be performed within 7 days prior to the planned start of the next cycle)

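### The PFS rule for subjects with no post-treatment scan lacks an alive condition, so read literally it censors at first dose a subject who dies unscanned, against the PFS definition

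*Protocol*

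**What the plan says.** Protocol section 7.3.2.3, under Progression-free Survival, gives three rules in close succession.

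- **Event.** PFS runs from the start of treatment "until the documentation of disease progression or death due to any cause, whichever occurs first".
- **General censoring.** The censoring date is the last assessment that shows no progression, for subjects "who have no documented progression and are still alive prior to data cutoff, dropout, or the initiation of alternate anticancer treatment".
- **No assessment.** "Subjects having no tumor assessments after the start of treatment with MEDI-565 will have PFS censored on the first date of treatment with MEDI-565".

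Under Time to Progression, the same section uses the no-assessment sentence with only the endpoint name changed.

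On timing, cycles last 28 days (section 3.1). On-treatment imaging follows every second cycle, and section 5.2.2.17 adds that "disease assessments must be performed within 7 days prior to the planned start of the next cycle". Section 5.2.2.18 requires a scan at the End of Treatment visit unless one was done within 14 days of discontinuation. Section 5.2.3.1 adds a 30-day scan for subjects who stopped without progression and have not started another anticancer therapy.

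**The concern.** The no-assessment sentence suits TTP, where death is not an event: a subject never scanned contributes no information on progression. For PFS it does not fit, because a death before the first scan is itself the event of interest. A programmer who follows the sentence literally would remove that death from the risk set at time zero.

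The subjects removed would be the earliest failures. The population has GI adenocarcinoma with no available standard or curative treatment, and entry requires a life expectancy of only three months (section 4.2.1), so some deaths before a first scan are plausible. The error has one direction: PFS looks better than it was. PFS is one of the measures named for antitumor activity, which the expansion phase is meant to examine further (section 3.4).

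**Working it through.** **The plan's own figures.** The protocol states no number for PFS. Its only efficacy design figure is about 80% power for ORR of 5% versus 20% with 20 subjects at one-sided 0.1 (section 7.5). A rule of at least 3 responders in 20 reproduces it: exact type I error 0.0755 and power 0.794. It does not involve PFS and does not change.

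**The three rules applied to one subject.** Take a subject who dies in week 5 with no post-treatment scan.

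| Rule in 7.3.2.3 | Result |
|---|---|
| Event definition | Event at week 5 |
| General censoring | Does not apply, because the subject is not alive |
| No-assessment sentence | Censored at first dose |

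The first two rows agree. The third contradicts them.

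**When this can arise.** Two cycles take 2 × 28 = 56 days, and the scan falls within the 7 days before the planned next cycle. The first scheduled scan is therefore at about Day 50 to 56, later if a cycle is delayed. A death before then falls under the sentence unless the subject already had an End of Treatment scan or another earlier scan.

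**Direction and size.** Let q be the share of subjects who die with no post-baseline scan, and assume no other censoring. Once those deaths have all occurred:

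- with deaths counted as events, S_correct(t) = (1 − q) × P(event-free beyond t among the rest);
- under the literal sentence, S_rule(t) = P(event-free beyond t among the rest).

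So S_rule(t) / S_correct(t) = 1/(1 − q).

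| Assumed q | Factor | A reported 50% should be |
|---|---|---|
| 5% | 1/0.95 = 1.05 | 0.95 × 50% = 47.5% |
| 10% | 1/0.90 = 1.11 | 0.90 × 50% = 45% |

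The protocol does not give q; these values only show the scale. Before the first-scan window the literal rule shows no drop at all for these deaths.

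**Illustration with 20 subjects (assumed data).** Two die unscanned before week 7, so q = 2/20 = 10%. Of the other 18, 9 progress at the week-8 scan.

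- Deaths counted: PFS is 18/20 = 90% at week 7 and 9/20 = 45% at week 8.
- Literal rule: PFS is 18/18 = 100% at week 7 and 9/18 = 50% at week 8.

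The ratio at week 8 is 50/45 = 1.11, as the formula gives.

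**The case against.** **A consistent reading exists.** The sentence follows directly after one limited to living subjects. It can be read as supplying the censoring date for living subjects who have no last assessment to use. That may well be what the authors meant. It bears on how serious the point is, but it does not remove it, because the sentence as written covers every subject without a scan.

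**The number affected may be small.** The rule reaches only subjects who die with no post-treatment assessment, not everyone who dies before week 8. Subjects who stop early should have an End of Treatment scan, some also have a 30-day scan, and section 5.3.7 allows additional measurements. Entry requires Karnofsky status of at least 70% and a life expectancy of at least three months. All of this stands. A reader might take an assumed survival median, count all deaths by week 8 and infer a large inflation. The documents do not support that: they give no survival or progression medians, and the calculation ignores the scans just listed.

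**Duration of response.** A reader might infer that DR is also wrong, since it is "the duration from the first documentation of objective response to the first documented disease progression" and a responder who dies without documented progression is censored at the last progression-free scan. The description is accurate, but ending DR at progression is a definition consistent with the protocol's TTP, not a contradiction. With ORR between 5% and 20%, an arm of 20 would have about 1 to 4 responders (20 × 0.05 to 20 × 0.20).

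**Postponed progression.** Section 5.1.1 says that "the investigator may postpone a diagnosis of PD until the next scheduled radiographic evaluation in the study" when the changes are believed to be drug-induced inflammation. A reader might infer that PFS, TTP and DR are therefore dated late. The protocol does not say which date counts if the next scan confirms progression. For PFS it says that "Disease progression is defined according to RECIST guidelines", which does not exclude the first qualifying scan. Section 7.1 leaves endpoint details to the SAP, where such a dating rule would commonly stand. No error is shown here.

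**Conclusion.** The point holds as an internal contradiction in the PFS rules. Taken literally, the no-assessment sentence turns a death before any scan into censoring at first dose, and PFS is then biased upward by 1/(1 − q) after the first-scan window. The factor assumes no other censoring, and its size depends on a q that the protocol does not supply. The direction follows from the text; the size does not.

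The weight is moderate to low. PFS is a secondary endpoint described by Kaplan-Meier, with no hypothesis, threshold or decision rule attached. DLT and MTD evaluation, the ORR test and OS are untouched. It is worth correcting because the protocol states the rule explicitly and an analysis that follows it inherits the error. A reader should not conclude that PFS and DR are overstated by a known amount.

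**What to change.** In section 7.3.2.3, replace the PFS no-assessment sentence with: *Subjects with no post-baseline tumor assessment who are alive are censored on the first date of treatment; subjects who die without a post-baseline assessment have a PFS event on the date of death.* Carry the same rule into the SAP. The TTP sentence can stay as it is.

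Optionally, report DR a second time with death from any cause as an event, beside the protocol's progression-only definition.

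The cost is one sentence. Dates of death are already needed for OS, so no new data, visits or subjects are required, and the sample size does not change. Reported PFS may be slightly lower.
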